## **9.9        QUALITY CONTROL**

In order to ensure the quality and integrity of data throughout the course of the study, proper quality control mechanisms and methods will be applied.

eCRF files from each participating site will be stored in CD-ROMs after completion of the study and will be distributed to the participating sites.

The investigators will be provided with a folder/file by the authorized representative of the study, in which they will be required to keep and store all study related documents. All study documents will be stored in this file by the Investigator. The contents of this file/folder may be subjected to audit/inspection by an authorized auditor, regulatory authorities or Institutional Review Boards (IRBs)

██████████ may conduct quality control visits of the study protocol and all related regulatory and BI procedures.

The Sponsor or designee (contracted CRO) will assure database quality by reviewing the data entered into the CRFs by investigational staff for completeness and accuracy, and in accordance with the data validation plan.

## **9.10        LIMITATIONS OF THE RESEARCH METHODS**

The basic limitations of the study relate to the general limitations that concern non - interventional studies. Since this study is a non - interventional study, it could be possible that different parameters which were not assessed and thus remain unknown, might lead to overestimating/underestimating/non-detection of differences of specific patients' characteristics. Selection bias on the patient level will be minimized by consecutive enrollment. Survival in IPF cohort studies is affected by the clinical characteristics and the related baseline patient conditions, as well as by the time interval between the diagnosis and the inclusion of the patient in the protocol. Patients that have been long diagnosed (at least more than 6 months before entering the study) with IPF and are included in the registry may be more likely to have a relatively more stable disease and/or better response in IPF management compared to the newly diagnosed patients; however, given the disease progression they will be in different disease stages. In this registry it will be possible to differentiate based on disease duration.

In case patient is lost to follow up, every effort will be made to contact the patient, keep him/her involved and if possible inquire about the reason of loss to follow-up. In order to assess the effect of loss to follow-up, percentages of dropouts will be summarized and patients will be characterized and compared to the remaining patients.

No re-evaluation of patients in this study is initially foreseen, something, that can lead to the conclusion that patients with overlapping diagnoses (like fibrosing interstitial pneumonia of unknown cause) have been included in the study, thus depicting the difficulties in differential diagnosis in clinical practice. However, given the fact that the participating sites are reference centers for IPF, and considering the eligibility criteria that apply for this study, the expected bias might be low.

The study is going to provide evidence regarding the situation in the IPF reference centers which are University Pulmonology Clinics and Pulmonology Clinics at Hospitals of Public Setting that follow up about 70%-80% of IPF patients in Greece.

Given the small numbers and the heterogeneous population no comparisons and causal associations can be assessed.

## **9.11 OTHER ASPECTS**

*Any other aspect of the research method not covered by the previous sections.*

### **9.11.1 Data Quality Assurance**

Monitoring visits will be performed to all participating sites, especially the ones that follow up large number of patients. During follow up visits the Study monitor will verify the documentation of the informed consent and will perform source data verification with the patient's medical records.

A quality assurance audit/inspection of this study may be conducted by the sponsor or sponsor's designees or by Institutional Review Board (IRBs) / Independent Ethics Committee (IECs) or by regulatory authorities. The quality assurance auditor will have access to all medical records, the investigator's study-related files and correspondence, and the informed consent documentation of this study.

### **9.11.2 Study Records**

The individual patient's Case Report Forms (CRFs) will be provided by the sponsor via an electronic data collection system (EDC).

Every doctor will have a study folder containing:

- The registry contract between the physician and [REDACTED]  
[REDACTED].
- The protocol
- The patient identification list (not allowed to be used off site)
- An approval letter by the Scientific Committee/Ethics Committee for the specific site
- Informed consent forms
- eCRF Sample printouts

#### **9.11.2.1    Source Documents**

Source documents provide evidence for the existence of the patient and substantiate the integrity of the data collected. Source documents are filed at the investigator's site.

Data entered in the eCRFs that are transcribed from source documents must be consistent with the source documents or the discrepancies must be explained. The investigator may need to request previous medical records or transfer records, depending on the study; also current medical records must be available.

For eCRFs all data must be derived from source documents.

#### **9.11.2.2    Direct Access to Source Data and Documents**

The investigator / institution will permit study-related monitoring, audits, IRB / IEC review and regulatory inspection, providing direct access to all related source data / documents. CRFs/eCRFs and all source documents, including progress notes and copies of laboratory and medical test results must be available at all times for review by the sponsor's clinical study monitor, auditor and inspection by health authorities (e.g. US Food and Drug Administration (FDA)). The Clinical Research Associate (CRA) / Clinical Monitor Local (CML) and auditor may review all CRFs/eCRFs, and written informed consents. The accuracy of the data will be verified by reviewing the documents described in [Section 9.11.2](#).

#### **9.11.2.3    Storage of Records**

Patient's files and other source documents must be kept for the maximum time period permitted by the hospital/institution or as defined below. The investigator must consult with the sponsor in case they wish to transfer the files to a third party, move them to a different location or if they are not capable of maintaining them for the defined period.

The investigator should keep the study files (e.g. source documents like medical files, contracts, electronic files and signed informed consent forms) for as long as it is defined by the applicable laws and regulations. The sponsor is responsible for maintaining the documents for at least 15 years. The archived data can be kept in electronic form so long as there are available backup copies in printed form, if it is required.

The participating sites are responsible for the archiving of the necessary documents/evidence for 15 years at least or for as long as it is required by the local legislation. Completion of study

#### **9.11.2.4    Completion of the Study**

The Institutional Review Board (Scientific/Administrative Board) in each participating hospital center needs to be notified about the end of the study (last patient out) or early termination of the study, unless it is differently required by the national regulations that govern the conduct of such studies in case these regulations have been amended until the completion of the study.

## **10. PROTECTION OF HUMAN SUBJECTS**

The study will be carried out in compliance with the protocol, the principles laid down in the Declaration of Helsinki, in accordance with the ICH Harmonized Tripartite Guideline for Good Clinical Practice (GCP) (to the extent applicable to the NIS setting and required by local regulations), Good Epidemiological Practice (GEP), Guidelines for Good Pharmacoepidemiology Practice (GPP), and relevant BI Standard Operating Procedures (SOPs). Standard medical care (prophylactic, diagnostic and therapeutic procedures) remains in the responsibility of the treating physician of the patient.

The investigator should inform the sponsor immediately of any urgent safety measures taken to protect the study subjects against any immediate hazard, and also of any serious breaches of the protocol/ICH GCP.

The rights of the investigator and of the sponsor with regard to publication of the results of this study are described in the investigator contract. As a general rule, no study results should be published prior to finalization of the Study Report, either interim or final.

### **10.1 STUDY APPROVAL, PATIENT INFORMATION, AND INFORMED CONSENT**

This study will be initiated only after all required legal documentation has been reviewed and approved by the respective Institutional Review Board (IRB) / Independent Ethics Committee (IEC) and Competent Authority (CA) according to national and international regulations. The same applies for the implementation of changes introduced by amendments.

More specifically, according to national regulatory requirements, both the protocol and the informed consent form (ICF) must be submitted to the Institutional Review Board (Scientific/Administrative Board) of the participating hospitals in order to be granted approval. The Scientific/Administrative Board of the participating hospitals must approve any amendment to the protocol or the ICF before the implementation of the amendment or the use of ICF, according to local regulations. The present non – interventional study will be conducted according to the applicable national regulatory requirements that govern the conduct of such clinical trials.

The informed consent form (ICF) will be provided to the study centers in the Greek language. It is the responsibility of the treating physician in the study center to receive the voluntary informed consent form from the patient (or their authorized representative) according to the national ICH/GCP guidelines and the regulatory and legal requirements for participation in the registry before entering any patient data in the eCRF.

Prior to patient participation in the study, written informed consent must be obtained from each patient (or the patient's legally accepted representative) according to ICH GCP and to the regulatory and legal requirements of the participating country. Each signature must be personally dated by each signatory and the informed consent and any additional patient-information form retained by the investigator as part of the study records. A signed copy of

the informed consent and any additional patient information must be given to each patient or the patient's legally accepted representative.

The patient must be informed that his/her personal study-related data will be used by Boehringer Ingelheim in accordance with the local data protection law. The level of disclosure must also be explained to the patient.

The patient must be informed that his / her medical records may be examined by authorized monitors (CML/CRA) or Quality Medicine auditors appointed by Boehringer Ingelheim, by appropriate IRB / IEC members, and by inspectors from regulatory authorities.

## **10.2 STATEMENT OF CONFIDENTIALITY**

Individual patient medical information obtained as a result of this study is considered confidential and disclosure to third parties is prohibited with the exceptions noted below. Patient confidentiality will be ensured by using patient identification code numbers.

Treatment data may be given to the patient's personal physician or to other appropriate medical personnel responsible for the patient's welfare. Data generated as a result of the study need to be available for inspection on request by the participating physicians, the sponsor's representatives, by the IRB / IEC and the regulatory authorities.

Patient's private data are going to be used by Boehringer Ingelheim and will be kept according to the requirements of the EU Data Protection Directive (95/46/EC) [\[22\]](#) guidelines and the national legislation regarding protection of private data. Data will be collected with the use of key codes. The identification codes will be used instead of patient names in order to protect patient identities when referring to registry data. The level of disclosure should also be explained to the patient.

Only authorized staff (hospital staff, sponsor representatives including monitors, authority representatives) will have access to patient's private data e.g. original source documents (medical records). The patient will agree to this specifically by providing informed consent and the appropriate statement will be included in the Informed Consent Form (ICF).

The physician must comply with the confidentiality policy as it is defined within the Registry Contractual Agreement. The physician will comply with the Protocol that has been approved by the Scientific Board/Ethics Committee. The physician is responsible for the conduct of all registry aspects in the study site and validates the integrity of all forwarded to the sponsor data with their signature.

## **11. MANAGEMENT AND REPORTING OF ADVERSE EVENTS/ADVERSE REACTIONS**

### **11.1 DEFINITIONS OF ADVERSE EVENTS**

#### Adverse event

An adverse event (AE) is defined as any untoward medical occurrence in a patient or clinical investigation subject administered a medicinal product and which does not necessarily have a causal relationship with this treatment. An adverse event can therefore be any unfavorable and unintended sign (e.g. an abnormal laboratory finding), symptom, or disease temporally associated with the use of a medicinal product, whether or not considered related to the medicinal product.

#### Adverse reaction

An adverse reaction is defined as a response to a medicinal product which is noxious and unintended. Response in this context means that a causal relationship between a medicinal product and an adverse event is at least a reasonable possibility. Adverse reactions may arise from use of the product within or outside the terms of the marketing authorisation or from occupational exposure. Conditions of use outside the marketing authorization include off-label use, overdose, misuse, abuse and medication errors.

#### Serious adverse event

A serious adverse event is defined as any AE which

- results in death,
- is life-threatening,
- requires in-patient hospitalization, or
- prolongation of existing hospitalisation,
- results in persistent or significant disability or incapacity, or
- is a congenital anomaly/birth defect

Life-threatening in this context refers to a reaction in which the patient was at risk of death at the time of the reaction; it does not refer to a reaction that hypothetically might have caused death if more severe.

Medical and scientific judgment should be exercised in deciding whether other situations should be considered serious reactions, such as important medical events that might not be immediately life threatening or result in death or hospitalization but might jeopardize the patient or might require intervention to prevent one of the other outcomes listed above. Examples of such events are intensive treatment in an emergency room or at home for allergic bronchospasm, blood dyscrasias or convulsions that do not result in hospitalization or development of dependency or abuse. Any suspected transmission via a medicinal product of an infectious agent is also considered a serious adverse reaction.

### Adverse Event of Special Interest (AESI)

No AESIs have been defined for this study.

## **11.2 ADVERSE EVENT AND SERIOUS ADVERSE EVENT COLLECTION AND REPORTING**

The investigator shall maintain and keep detailed records of all AEs in their patient files.

### Collection of AEs

The study design is of non-interventional nature and the study is conducted within the conditions of the approved marketing authorisation. Sufficient data from controlled interventional trials are available to support the evidence on the safety and efficacy of Nintedanib. For this reason the following AE collection and reporting requirements have been defined.

The following must be collected by the investigator in the (e)CRF from signing the informed consent onwards until the end of the study:

- all ADRs related to Nintedanib, taken for idiopathic pulmonary fibrosis (serious and non-serious),
- all AEs with fatal outcome in patients exposed to Nintedanib, taken for idiopathic pulmonary fibrosis

All ADRs, including those persisting after study completion must be followed up until they are resolved, have been sufficiently characterized, or no further information can be obtained.

The investigator carefully assesses whether an AE constitutes an ADR using the information below.

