Name of active ingredient: Not applicable			
Protocol date: 29 August 2016	Study number: 1199.252	Version/Revision: 1.10	Version/Revision date: 22 February 2018
Research question and objectives:	
The main objective of this IPF registry is to gain further knowledge on the characteristics, management, progression and outcomes of patients with IPF as treated under real-world, clinical practice conditions in Greece.
 
More specifically, this registry is going to:
 

• Provide a comprehensive clinical picture for IPF

• Track access to health care and cost of caring for IPF patients over time

• Examine the implementation of treatment guidelines [2] used on patients diagnosed with IPF, according to the existing diagnosis guidelines [1]

 
Characterization of patients on different treatments
		
Study design:	
National, multi-center, observational disease registry based on new data from a significant sample size of IPF patients in Greece.
 
Patients will be followed up for 2 years and information will be collected during this time period. This is a non-interventional study and primary data collected during study visits will be used.
		
Population:	
About 300 patients are going to be included in the study in a consecutive manner, coming from seven (7) Centers in Greece – University Pulmonology Clinics & Reference Centers of Public Hospital Setting – that follow up around 70% - 80% of IPF patients within the Greek territory from April 2017 to April 2019.
 
To be eligible for participation in the study patients must fulfill ALL the inclusion criteria and NONE of the exclusion criteria that are listed below:
 
Inclusion Criteria
 

• Newly diagnosed (less than 6 months) or patients previously diagnosed with IPF (more than 6 months prior to baseline visit), based upon the consensus statement jointly issued by ATS/ERS/JRS/ALAT in 2011 (see Annexes 6 and 7 on HRCT and histological criteria in Annex 6).

- Exclusion of other known causes of ILD (e.g., domestic and occupational environmental exposures, connective tissue disease, and drug toxicity)

- Evaluation of IPF with HRCT or combinations of HRCT and surgical lung biopsy, if available

		

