
other percentages, and as mean value with standard deviation (SD), along with minimum and maximum values. Categorical values will be listed as absolute and relative frequencies.
 
Stratified analyses will be performed among newly diagnosed patients as well as patients that were diagnosed in the past. For outcome analysis the newly diagnosed patients are the decisive one. Due to the limited number of patients and population heterogeneity, no causal relationship conclusion can be derived (no hypothesis testing). Statistical analyses will be performed with IBM SPSS Statistics (Version 19.0).
			
Milestones:	
Data collection start: April 2017
 
Data collection end: June 2021
 
Final report of trial results: June 2022
		

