### **9.3.3      Study Visits**

The registry is scheduled to run for 4 years in total (2 years recruitment + 2 years follow up) (April 2017 to April 2021).

During the follow up period, data will be collected on standard clinical visits which usually are scheduled around: 3-months (+/- 1 month), 6-months (+/- 1 month), 12-months (+/- 2 month), 18-months (+/- 2 month) and 24 months (+/- 2 months), until the end of participation in the study. In case of events, unscheduled visits may be required.

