## **9.5 DATA SOURCES**

The study will mainly include the recording of new data through a web based system for data collection. Data will be collected by the study doctors as they occur according to standard clinical practice in the approximate visiting schedule indicated above.

Source (primary) patient data related to their medical and IPF history will be collected by the investigators from the patient's medical files/records and will be documented in the relevant eCRF section.

Data regarding treatment modifications, concomitant treatments, study related routine clinical assessments, adverse events (ADRs) and survival status will also be collected. If a patient withdraws early from the study, they will be contacted via telephone at the end of the Study in order to evaluate their survival status. Another follow-up assessment should be performed if possible (unless reason for discontinuation is erroneous enrolment of the patient into the study at baseline), and data should be entered on the eCRF of the next planned visit unless the patient has actively withdrawn consent for any kind of future contacts.

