**7.8 SAFETY ANALYSIS****7.8.1 Adverse events**

Safety analysis will be performed in the FAS population. No stratified analysis for safety will be considered. All adverse events will be coded according to MedDRA dictionary.

The analyses of adverse events (AEs) will be descriptive in nature. All analyses of AEs will be based on the number of subjects with AEs and NOT on the number of AEs.

The frequency of subjects with adverse events following the ICF signature will be summarized according to primary system organ class and preferred term (MedDRA version to be displayed in the tables). System organ classes will be sorted alphabetically, preferred terms will be sorted by frequency (within system organ class).

Summary statistics will be provided for the following categories: all AEs, all SAEs and AEs with causal relationship to BI medication. AE listings will also be provided.

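### No single end of observation: nintedanib reactions and fatal events are collected to study end, visits stop at month 24, and the SAP sets no cut-off for adverse-event percentages or survival curves

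*Protocol*

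**What the plan says.** **Patient-level end.** The protocol abstract says: "Patients will be followed up for 2 years and information will be collected during this time period". Section 8 repeats the two years. Section 9.3.3 places the last visit at "24 months (+/- 2 months), until the end of participation in the study". Table 1 marks survival status only in the follow-up column, and its footnote defines that column as the five visits from month 3 to month 24.

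**Open-ended follow-up.** Protocol 9.4 treats two years as a minimum. For all patients it names death, transplantation, withdrawal of consent and study end as the stopping points. Section 9.5 adds a survival check: "If a patient withdraws early from the study, they will be contacted via telephone at the end of the Study". That call covers early withdrawals on any drug, but not patients who complete month 24.

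**Study-level end for some events.** Section 11.2 sets the rule "The following must be collected by the investigator in the (e)CRF from signing the informed consent onwards until the end of the study" for nintedanib reactions and for "all AEs with fatal outcome in patients exposed to Nintedanib, taken for idiopathic pulmonary fibrosis". Section 9.11.2.4 says the hospital board "needs to be notified about the end of the study (last patient out", which ties study end to the last patient. The abstract gives "Data collection end: June 2021" (5 June 2021 in section 6), whereas section 9.3.3 ends the registry in April 2021.

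**Analysis.** SAP 7.8.1: "The frequency of subjects with adverse events following the ICF signature will be summarized according to primary system organ class and preferred term". The unit is the subject and the set is the unstratified FAS; SAP 7 presents categorical data as counts and percentages. Protocol 9.8.1 instead promises incidence rates with 95% confidence intervals for all events during follow-up. SAP 4 adds Kaplan-Meier curves with no administrative censoring date. SAP 6.7 excludes unscheduled visits from the primary and secondary endpoints, which include vital status (SAP 5.1), but uses them for adverse events.

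**The concern.** Two analyses depend on when observation stops, and neither has a stated stop.

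The first is the adverse-event percentage. If collection runs to the calendar end of the study, an early enrolee is observed for about twice as long as a late one. A plain percentage of subjects then pools unequal windows and cannot be read as a two-year risk.

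The second is survival. If follow-up is fixed at two years, completers not exposed to nintedanib have no scheduled vital-status collection after month 24. Fatal events in exposed patients must still be reported. Deaths would enter after month 24 without the matching survivors, and Kaplan-Meier estimation is not valid when being observed depends on having died. SAP 6.7 adds to this: at a late unscheduled contact an adverse event counts, but being alive does not.

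**Working it through.** **1. Windows.** Inputs: data collection starts 5 April 2017 and ends 5 June 2021 (protocol 6); enrolment April 2017 to April 2019 (9.6); last visit 24 ± 2 months (9.3.3).
- The plan's own figure: 24 + 24 = 48 months, April 2017 to April 2021. Reproduced.
- First patient to 5 June 2021: 50.0 months. A patient enrolled 5 April 2019: 26.0 months. Mean under uniform enrolment: (26 + 50)/2 = 38.
- To April 2021: 24 to 48 months, mean 36.
- If collection stopped at the last visit: 22 to 26 months for every completer.

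April 2019 plus 26 months is June 2021, so the milestone is the upper edge of the last patient's visit window.

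**2. Effect on a reaction percentage.** Assumptions: constant hazards, uniform enrolment, windows 26 to 50 months, and an illustrative 20% risk at month 24.
- *Ignoring death:* h = −ln(0.8)/24 = 0.00930 per month. The pooled value is 1 − (e^(−26h) − e^(−50h))/(24h) = 1 − 0.157/0.223 = 29.6%. It is 21.5% for a 26-month window and 37.2% for a 50-month window.
- *Death as a competing event:* with death hazard d = ln2/median and reaction hazard a, the cumulative incidence is a/(a+d) × (1 − e^(−(a+d)t)). Choose a so that this equals 20% at t = 24, then average over 26 to 50 months.

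| Median survival | d | a | Pooled percentage |
|---|---|---|---|
| 24 months | 0.0289 | 0.0132 | 24.8% |
| 36 months | 0.0193 | 0.0118 | 26.1% |

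The medians are the two to three years in protocol 7.4, which says that this may be an underestimate.

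**3. How many deaths fall in the gap.** With final visit v and window w, the share dying between them is e^(−hv) − e^(−hw), here with h = ln2/median, averaged over w from 26 to 50. A 24-month median with v = 24 gives 16.0% (about 48 of 300). An assumed 60-month median with v = 26 gives 9.4% (about 28 of 300). These cover all treatments. The documents do not give the share exposed to nintedanib; if it were half, about 14 to 24 deaths would be reportable under 11.2.

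**4. Effect on the survival curve, fixed two-year reading.** Simulation: 36-month median, half of patients exposed, final visits near month 24. All deaths up to that visit are recorded, then only deaths in exposed patients, and all survivors are censored at the visit. The true values are e^(−ln2 × 24/36) = 63% at month 24 and 50% at month 36. The curve still reads about 63% at month 24, but about 17% at month 36. The reason is simple: once the survivors have left, the risk set holds only patients who go on to a recorded death.

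**The case against.** **Protocol 9.4 follows everyone to study end.** This stands as text. A reader might infer that vital status stops at month 24 and that late deaths are recorded for nintedanib users only. The documents do not support that: 9.4 sets the same stopping rule whatever the drug, and 9.5 calls early withdrawals on any treatment. Section 11.2 adds no visit after month 24 either, so it is no more operational than 9.4. What remains is that 9.4 contradicts the fixed two years elsewhere, and no procedure is scheduled to collect survival from completers after month 24.

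**The protocol already plans incidence rates.** True, and person-time would deal with unequal windows. But SAP 7.8.1 does not carry the rates forward, and person-time also needs a defined end.

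**Kaplan-Meier handles unequal follow-up.** Only when censoring is unrelated to outcome. On the fixed two-year reading it is not, although the part of the curve before about month 24 is essentially safe.

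**No treatment comparison is planned.** Correct. A reader might infer that mortality is biased against nintedanib, or that a fatal-event table will disagree with the survival analysis. Neither output is planned: protocol 9.8.1 rules out treatment comparisons, SAP 7.8.1 rules out stratified safety analysis and names no fatal-event summary, and SAP 4 describes curves for the patients in the study.

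**A month-24 cut-off discards survival data that 9.4 calls for.** Fair. Hence the sections must be reconciled first. A longer curve would be usable only if vital status were collected from all completers alike.

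**Conclusion.** The point holds as an inconsistency with a concrete analytic consequence. The protocol gives three different ends of observation, and the SAP chooses none for adverse events or survival.

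Read literally, completers' adverse-event windows run about 26 to 50 months (24 to 48 to April 2021). They are longer for earlier enrolees, so the expected percentage falls, not rises, with later enrolment. Patients who die, receive a transplant or withdraw have shorter windows.

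A 20% two-year reaction risk would read about 25–26%, and 30% is the upper value if death is ignored. Both figures assume constant hazards, uniform enrolment and collection that really continues to June 2021. A reaction hazard that falls over time, patients stopping the drug, or sites that stop collecting at month 24 would make the gap smaller.

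The survival distortion arises only if follow-up is fixed at two years. It is then confined to the curve beyond about month 24, where it can be large. The 17% against 50% at month 36 is an illustration that depends on the assumed exposed half and on complete reporting of late deaths in that half.

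**What to change.** 1. **Protocol:** reconcile the abstract, sections 8, 9.3.3 and 9.4, and section 11.2, and state one end of observation for analysis. Leave the safety-reporting duty in 11.2 as it is.
2. **SAP 7.8.1:** count adverse events, including fatal ones, only up to each patient's month-24 visit (within its window) or earlier exit, by the same rule whatever the drug. Put later reports in a separate listing.
3. **SAP 4:** count deaths to the same cut-off, censor survivors there, and end the displayed curve there.
4. **SAP 7.8.1:** add the incidence rates with 95% confidence intervals promised in protocol 9.8.1, with person-time to the same cut-off. SAP 6.6 leaves adverse-event dates unimputed because no time-based analysis of them is planned, so it needs a line on incomplete onset dates.

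Cost: a few sentences in the SAP, a protocol clarification and one set of rate tables. No new data are needed. The downside is that late events move from the tables to a listing, and the curve makes no statement beyond about two years.
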